# 4.3 Subject Withdrawal Criteria

## 4.3.1 Premature Discontinuation of Study Treatment

The criteria for premature discontinuation of study treatment with immunosuppressive medication are detailed in section 6. Subjects who prematurely discontinue treatment with study drug will remain in the study until normal termination. They will be followed to monitor safety and efficacy parameters. Data from these subjects will be used in the intent-to-treat analysis.

#### 5. STUDY TREATMENT REGIMEN

Please refer to section 1.5, and to applicable product labeling for known and potential risks to human subjects associated with the study treatment regimen.

All immunosuppressant medications described in this protocol are FDA approved for use in solid organ transplantation except for rituximab (Rituxan®, IDEC Pharmaceuticals Corp., San Diego, CA and Genentech, Inc., San Francisco, CA), which is licensed for use in B-cell non-Hodgkin's lymphoma and rheumatoid arthritis. Please refer to sections 1.14 for discussions of the mechanism of action and associated risks, respectively, of each proposed immunotherapy agent. Each immunosuppressant medication will be prepared and administered as licensed, and the dosage will follow that detailed in section 3.0.

[figure not shown]

Figure 2: Islet transplant and immunosuppression regimen

# 5.1 Investigational Agent: Allogeneic Islets

## **5.1.1** Formulation, Dosage, and Administration

The final product is a 200 mL sterile suspension of  $\geq$ 70% viable,  $\geq$ 30% pure, allogeneic human purified islets in 2.5% human serum albumin (HSA), 25mM Hepes for administration by intraportal infusion. The final product is supplied in 600 mL Ricordi® bags, containing a dose of  $\geq$ 5,000 IEQ/kg recipient body weight (BW) for the first infusion, and  $\geq$ 4,000 IE/kg recipient BW for subsequent infusions.

Component	Quantity per Batch
Purified Human Pancreatic Islets	≥4.0 x 10  IEQ  /kg recipient BW  (total IEQ/infusion)
CIT Transplant Media 	≤600 mL 
Human Serum Albumin (HSA), USP	2.5%
HEPES Buffer, USP	25 mM

*Table 1: Composition of final drug product [Product Code: PHPI-A-01]* 

#### **Administration:**

The islet mixture is delivered slowly via gravity drainage from a bag attached to the catheter in the portal vein or port vein tributary. Access to the portal vein is achieved by percutaneous transhepatic access under fluoroscopic, ultrasonographic, or real-time CT guidance. Alternatively, access to a mesenteric or omental venous tributary of the portal vein can be obtained by mini-laparotomy under general anesthesia (transplant site preference or in the extremely rare circumstance that percutaneous access cannot be achieved).

At a minimum, portal pressure will be monitored before and after infusion of each bag of the islet product, as well as after the final wash. Portal pressure measurements will be documented in the medical record.

Additional guidelines for islet administration and portal pressure measurements are located in the Manual of Procedures; however each participating site should follow its site-specific standards to ensure compliance with institutional and subject safety.

#### 5.1.2 Drug Accountability

Under Title 21 of the Code of Federal Regulations (21CFR §312.62) the investigator is required to maintain adequate records of the disposition of the investigational agent, including the date and quantity of the drug received, to whom the drug was dispensed (subject-by-subject accounting), and a detailed accounting of any drug accidentally or deliberately destroyed.

Records for receipt, storage, use, and disposition will be maintained by the study site. A drugdispensing log will be kept current for each subject. This log will contain the identification of each subject and the date and quantity of drug dispensed.

All records regarding the disposition of the investigational product will be available for inspection by the clinical trial monitor.

<sup>1 IEQ = Islet Equivalents

<sup>2 BW = Body Weight

<sup>3 600 mL maximum total volume in Ricordi® infusion bags containing 200 mL each

# 5.2 Immunosuppression Medications

#### 5.2.1 Initial Allogeneic Islet Transplant

Please refer to applicable product labeling and Package Inserts for known and potential risks to human subjects associated with the consensus immunosuppressive medications.

#### 5.2.1.1 Rituximab

Rituximab will be used at a dose of 375 mg/m² per injection administered twice, one week apart. This is less than the recommended dose used for non-Hodgkin's lymphoma in humans, which is 375 mg/m² per injection administered four times at weekly intervals, and is less than the recommended dose used for the treatment of rheumatoid arthritis, which is 1000 mg twice, 15 days apart³¹. In addition, this dose lead to sustained (> 6 months) B lymphocyte depletion, and caused a low (4.3%) incidence of human antichimeric antibody formation³¹. The proposed rituximab dose for CIT-05 is based on the pre-clinical non-human primate trial in allo-islet transplantation that utilized two doses of 375 mg/m² and achieved long-term islet allo-graft survival associated with B lymphocyte depletion that persisted for over 3 months¹⁵⁶. Similarly in solid organ transplantation, rituximab has been used off-label for the prevention and treatment of rejection with rituximab 375 mg/m² given as one to four doses. It has been established that the use of one or two doses of 375 mg/m² leads to B lymphocyte depletion and assures safety in patients with high-titer PRA experiencing kidney allograft rejection and awaiting kidney transplantation .

The first dose of rituximab will follow the first ATG infusion between day -2 and day -1 relative to transplant (please see below); the second doses of rituximab will occur on day +6 (±1). Acetaminophen 650 mg and diphenhydramine 50 mg will both be administered orally 30 minutes before the start of each rituximab infusion. Because infusion reactions generally occur only with the first dose of rituximab, the first dose will follow the initial dose of Thymoglobulin® where 2 mg/kg of intravenous methylprednisolone is given concurrently. Administration of this high dose of glucocorticoid should mitigate the incidence and severity of infusion reactions. Should a severe infusion reaction occur with the initial dose of rituximab, the subsequent dose will be administered with 0.5 mg/kg of methylprednisolone intravenously 30 minutes before infusion. In rheumatoid arthritis, only 36% of patients experience an infusion reaction with the initial dose of rituximab, and the majority of these were classified as mild-to-moderate, consisting of transient hypo- or hypertension, cough, pruritis, and rash.

#### 5.2.1.2 Rabbit Anti-thymocyte globulin (ATG, Thymoglobulin®)

A total of 6 mg/kg will be given as an IV infusion over 8 hours on days -2, -1, 0, +1, and +2. The dose will be 0.5 mg/kg on day -2, 1.0 mg/kg on day -1, and 1.5 mg/kg on days 0, +1, and +2. The first dose will be administered over 8 hours and subsequent doses will be administered over 6 hours. The dose of thymoglobulin may be reduced or eliminated on any day at the discretion of the treating physician for any subject safety concerns that may arise. Premedications will be used as follows:

- #1: Acetaminophen (Tylenol®) 650 mg PO/PR ½ hr before and midway through ATG infusion
- #2: Diphenhydramine (Benadryl®) 50 mg PO ½ hr before and midway through ATG infusion
- #3: Methylprednisolone (Solu-Medrol®) 1 mg/kg IV one hour prior to and midway through the first ATG infusion only (*i.e.* on day –2)
- #4: Pentoxifylline (Trental®) 400 mg PO TID to be initiated one hour prior to the first ATG infusion and to be continued through day +7

If the subject is admitted when the vascular access team is not available or at a time when the placement of a Peripherally Inserted Central Catheter could delay the first Thymoglobulin® dose, it may be administered IV via a peripheral line as follows:

- Dilute the Thymoglobulin® in 500 cc Normal Saline (not D5W)
- Combine with Heparin 1000 units and Hydrocortisone 20 mg.

# 5.2.1.3 Sirolimus (Rapamune®)

Sirolimus will be administered at an initial dose of 0.2 mg/kg PO on day -2 relative to islet transplant, followed by 0.1 mg/kg QD. The daily dose will be adjusted to the whole blood 24-hr trough to target, as tolerated, 12-15 ng/mL for the first 3 months and 10-12 ng/mL thereafter. If a subject develops intolerable or clinically undesirable side-effects related to sirolimus therapy, his/her therapy may be converted to maintenance mycophenolate mofetil (MMF) at the discretion of the principal investigator.

# 5.2.1.4 Tacrolimus (Prograf®)

Tacrolimus may be used as a replacement for sirolimus if sirolimus is not tolerated. Tacrolimus will be administered at an initial dose 0.015 mg/kg PO BID with the whole blood 12-hr trough adjusted to 6-10 ng/mL. Should subjects experience a decrease in their GFR of  $\geq$ 33% compared with baseline, a nephrology consult will be obtained, and tacrolimus target trough levels will be reduced by 25% should CNI toxicity be suspected as the primary cause for the decline in renal function.

# 5.2.1.5 Cyclosporine, USP (Neoral®)

Cyclosporine may be used as a replacement for tacrolimus if clinically indicated. Cyclosporine will be administered at an initial dose of 6 mg/kg/d in 2 divided doses, with target levels of 150-200 ng/mL.

# 5.2.1.6 Mycophenolate Mofetil (CellCept®)

Mycophenolte mofetil may be used if sirolimus levels cannot be maintained  $\geq 10$  ng/mL. Mycophenolate mofetil will be administered at a dose of 500 to 1500 mg PO BID in addition to either tacrolimus or sirolimus. Subjects must practice two methods of contraception while taking MMF. If a subject experiences severe neutropenia (absolute neutrophil count  $<1x10^9/L$ ) while taking mycophenolate mofetil, mycophenolate mofetil exposure will be reviewed and

mycophenolate mofetil administration will be adjusted as part of the study protocol's neutropenia management plan.

# 5.2.1.7 Mycophenolate sodium (Myfortic®)

Mycophenolate sodium may be used as a replacement for tacrolimus, sirolimus, or mycophenolate mofetil. Mycophenolate sodium will be dosed at 360 to 720 mg PO BID. Subjects must practice two methods of contraception while taking Myfortic®.

## **5.2.2** Subsequent Allogeneic Islet Transplants

The immunosuppressive regimen for subsequent islet transplants will be identical to the regimen for the initial islet transplant with the following exceptions.

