#### 1.4.4 Induction Immunosuppression for Subsequent Islet Transplants

The immunosuppressive regimen for subsequent islet transplants will be identical to the regimen for the initial islet transplant with the exception of Thymoglobulin®. Daclizumab or basiliximab will be used instead of Thymoglobulin® for all subsequent islet transplants.

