In December 2006 the FDA posted an alert concerning the safety of rituximab therapy for systemic lupus erythematosus (SLE). This alert was based on the occurrence of two deaths caused by progressive multifocal leukoencephalopathy (PML) in SLE patients who had received repeated courses of rituximab in addition to past cytotoxic medications, including cyclophosphamide. PML is a rare but often fatal disease caused by reactivation of latent JC virus in immunocompromised patients, such as those with advanced HIV and those who have received chemotherapy with or without bone marrow transplantation. PML has been reported in 24 other cases of SLE with no exposure to rituximab. PML has occurred in 23 patients treated with rituximab for hematologic malignancies who also received chemotherapy and sometimes hematopoietic stem cell transplantation. The manufacturer of rituximab, Genentech, estimates that  $\sim 10,000$  patients with SLE have been treated with rituximab, and that  $\sim 250,000-1,000,000$  patients all together have received rituximab. An expert review committee compiled by the NIDDK/Trial Net that oversees the use of rituximab in studies of recent-onset type 1 diabetes concluded that the present data do not support a causal relationship between rituximab and PML.

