Intraportal delivery of islets isolated from cadaveric donors will be achieved using a transperitoneal approach through a mini-laparotomy. Islets will be ABO compatible and have a negative serum crossmatch for T lymphocytes, but HLA matching will not be required. It is estimated that >600,000 IEq will be required per recipient at an average of 9,000 IEq/kg of recipient body weight to achieve insulin independence. To optimize the chance of achieving insulin-independence with no more than two procedures, islet preparations  $\geq$ 5,000 IEq/kg will be used for the first infusion, and islet preparations  $\geq$ 4,000 IE/kg will be used for subsequent infusions. The quantity of tissue transplanted will be < 7 mL per infusion. Quality control testing will include assessment of islet purity (> 30%), viability (> 70%), sterility (negative gram stain), and endotoxin content (< 5 IU/kg recipient) prior to release. Functional assessment of islets will also be performed.

Islets will be infused together with heparin and ciproflaxin (70 U/kg) with periodic portal pressure monitoring. Heparin will be continued for 48 hours after the procedure as an intravenous drip with target PPT levels of 50-60 seconds. Following completion of heparin, subjects will be treated with enoxaprin 30 mg subcutaneously bid through day 7.

Subjects who do not meet criteria for insulin-independence at any time after 75 days following the initial transplantation may be eligible for a second transplantation of islets. If the development of panel-reactive anti-HLA antibodies has occurred, only subjects with a PRA ≤ 20% will remain eligible, and both antibody specific and prior mismatched antigens will be avoided. To avoid problems related to Thymoglobulin® sensitization, we will administer daclizumab (2 mg/kg on day 0 followed every two weeks with 1 mg/kg for 4 additional doses) in order to sustain an anti-T lymphocyte induction effect. Should a third infusion of islets occur to achieve insulin-independence, only if the interval between the second and third islet infusions is >10 weeks will an additional course of daclizumab be administered. Rituximab administration will not be repeated with either a second or third infusion of islets.

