## 5.2.2.1 Monoclonal Antibody IL-2 Receptor Blocker

All subjects will receive one of the following monoclonal antibody IL-2 receptor blockers: daclizumab or basiliximab

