Hospital discharge is anticipated by Day +2, after which four weekly followed by four biweekly clinic visits will occur for the first 3 months to monitor glucose, electrolytes, creatinine, LFTs, CBC and differential, and trough levels of tacrolimus and rapamycin, and to titrate insulin therapy based on prior week's 4-7 daily BG measurements (pre- and 2-hours post-meals and bedtime). BG targets will be < 110 mg/dL fasting and < 140 mg/dL after meals for the first month, followed by < 126 mg/dL fasting and < 180 mg/dL after meals thereafter. Insulinindependence (defined in Section 3.1.1) will be determined at  $75 \pm 5$  days post-transplant based in part on the ability to achieve those latter glycemic targets.

Subjects who do not meet the criteria for insulin-independence at any time after 75 days following the initial transplantation will be eligible for a second (or third) transplantation of islets from one or more donor pancreata, unless sensitization to donor antigen, as indicated by the development of >20% panel-reactive anti-HLA antibodies, has occurred. A similar procedure for hospital admission will be followed for a subsequent infusion of islets, except that daclizumab will replace Thymoglobulin® and start on Day 0; thus, no period of islet culture will be required. Post-infusion care will be identical for the first 2 months.

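### Sections 1.4.4 and 5.2.2, read literally, repeat rituximab at second and third transplants, while section 3 says it is not repeated; no rule says which section governs

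*Protocol*

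**What the plan says.** Rituximab is the first item under section 5.2.1, the regimen for the initial transplant: "Rituximab will be used at a dose of 375 mg/m² per injection administered twice, one week apart" (section 5.2.1.1).

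The protocol describes the regimen for later transplants in five places:

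- **Section 5.2.2:** "The immunosuppressive regimen for subsequent islet transplants will be identical to the regimen for the initial islet transplant with the following exceptions". The only exception that follows is in 5.2.2.1: "All subjects will receive one of the following monoclonal antibody IL-2 receptor blockers: daclizumab or basiliximab". Rituximab is not mentioned.
- **Section 1.4.4:** "The immunosuppressive regimen for subsequent islet transplants will be identical to the regimen for the initial islet transplant with the exception of Thymoglobulin". An IL-2 receptor blocker takes its place. Rituximab is not mentioned.
- **Synopsis, Treatment Description:** rituximab is given with Thymoglobulin, and only Thymoglobulin is swapped for the second and third transplants.
- **Section 7.5:** daclizumab replaces Thymoglobulin, and treatment will "start on Day 0; thus, no period of islet culture will be required". Rituximab is not mentioned.
- **Section 3:** "Rituximab administration will not be repeated with either a second or third infusion of islets".

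**The concern.** Rituximab is the agent under study. Only section 3 names it in connection with later transplants, and it excludes repetition. The two sections that define the later regimen as identical to the first leave rituximab in, because neither lists it as an exception. Someone working from section 5.2.2, which was written for later transplants, could give a second course. Someone working from section 3 would not.

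If re-transplanted subjects were treated under different rules, several summaries would mix different exposures to the study drug: related adverse events, rituximab levels, anti-rituximab antibodies, B-cell depletion and recovery, and efficacy at Day 365 and after the final transplant. The secondary comparisons with CIT-07 draw on many of the same outcomes. With 12 subjects planned, a few such cases would be a sizeable share of any subset.

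**Working it through.** No sample size or power figure is involved. The check compares the texts and then counts doses.

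**1. What each place implies for rituximab at a second or third transplant**

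| Place | Text on later transplants | Rituximab repeated? |
|---|---|---|
| Section 5.2.2 | Same as initial; IL-2 receptor blocker the only listed exception | Yes, by implication |
| Section 1.4.4 | Same as initial; Thymoglobulin the only exception | Yes, by implication |
| Synopsis | Only Thymoglobulin swapped | Yes, by implication |
| Section 7.5 | Only the Thymoglobulin replacement named | Not addressed |
| Section 3 | Rituximab named and excluded | No, expressly |
| Sections 1.4.2 and 2.2 | Rituximab placed in the initial induction | Leans to no |
| Opening of section 5 | Dosage refers back to section 3.0 | Leans to no; no precedence stated |
| Appendix 1 | Schedule restarts at Day 0 for each transplant; it has rows for rituximab PK and anti-rituximab antibodies | Does not settle it |

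**2. Can an identical regimen be carried out?** Section 5.2.1.1 places the first rituximab dose after the first ATG infusion, between Day -2 and Day -1. It relies on the methylprednisolone given with that infusion to limit infusion reactions. Under 1.4.4 and 7.5, later transplants use no ATG, and 7.5 starts the replacement agent on Day 0. A repeated first dose would therefore have no ATG infusion to follow and no stated steroid cover. The initial sirolimus dose in 5.2.1.3 is also dated Day -2, and 5.2.2 does not say whether it applies again.

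**3. Planned cumulative dose** = courses × 2 doses × 375 mg/m² (dose from 5.2.1.1)

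- Section 3, any number of transplants: 1 × 2 × 375 = 750 mg/m².
- Sections 1.4.4 and 5.2.2 read literally, after a second transplant: 2 × 2 × 375 = 1,500 mg/m².
- The same, after a third transplant: 3 × 2 × 375 = 2,250 mg/m².
- Ratios to section 3: 1,500/750 = 2 and 2,250/750 = 3.

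**4. Which results are touched?** Section 7.5.1 considers a second transplant only after the 75 ± 5 day visit and its metabolic assessment. The primary endpoint, at 75 ± 5 days after the first transplant, is therefore fixed before the conflict can arise. The same section closes eligibility at 8 months after the first transplant. In a re-transplanted subject, the Day-365 assessment after the first transplant therefore always follows the re-transplant, as do all after-final-transplant assessments.

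**The case against.** The strongest case on the other side is that the protocol does answer the question. Only section 3 addresses rituximab at later infusions by name, and it is unambiguous. Repetition is an inference from the word identical plus silence. Section 5 opens by sending the reader to section 3.0 for dosage. Sections 1.4.2 and 2.2 tie rituximab to the initial induction, and 5.2.1.1 ties its first dose to an ATG infusion that later transplants do not have. The exception list in 5.2.2 is also plainly incomplete: it never names Thymoglobulin, so the same literal reading would repeat that drug too.

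Much of this stands. The texts are not evenly balanced, and the chance that a site would re-dose is lower than the wording of 5.2.2 alone suggests. It does not remove the conflict. No sentence gives section 3 precedence over 5.2.2, and section 3 cannot simply be assumed to be the controlling text. For example, it sets the PRA limit for a second transplant at 20%, while 7.5.1 sets 50%; and it gives pentoxifylline for 4 weeks, while 5.2.1.2 and 5.3.2.3 stop at day 7. An incomplete exception list in 5.2.2 is itself part of the defect. The regimen diagrams are not shown in the copy reviewed, so whether they address the point is unknown.

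Two stronger readings are tempting, and the documents support neither:

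- **Safety.** A reader might infer from section 1.5.2.3 that the protocol ties PML deaths to repeated dosing, because it mentions "SLE patients who had received repeated courses of rituximab". The same text says those patients had also had cytotoxic drugs, and it ends with an expert committee's view that the data do not support causation.
- **Dose justification.** A reader might infer that the comparison with the lymphoma course (4 × 375 = 1,500 mg/m²) fails at a second transplant. Section 5.2.1.1 compares the two-dose course for the initial transplant and makes no claim about totals across transplants.

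**Conclusion.** The contradiction is real and stands in the current text. Sections 1.4.4 and 5.2.2, supported by the synopsis, carry rituximab forward by implication, and section 3 excludes it expressly. Planned exposure to the study drug in a re-transplanted subject differs by a factor of 2 (second transplant) or 3 (third). Separately, the identical-regimen wording cannot be followed as written, because items tied to Day -2 and to ATG have no counterpart at a later transplant.

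The scope is limited. The primary endpoint and subjects with one transplant are unaffected. The affected results are the safety, PK, anti-rituximab antibody, B-cell, Day-365 and after-final-transplant outcomes in re-transplanted subjects. The protocol does not say how many of the 12 are expected to be re-transplanted, so the number affected could be anywhere from 0 to 12. The 2,250 mg/m² figure also requires a third transplant, which section 7.5.1 allows only if ten conditions are met. The dose totals assume full planned courses.

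**What to change.** The sponsor should reconcile the synopsis and sections 1.4.4, 5.2.2 (with 5.2.2.1) and 7.5 with section 3, so that one rule on rituximab at second and third transplants stands throughout. Section 5.2.2 should then state explicitly, for rituximab and for each other item dated Day -2 in section 5.2.1, whether it applies at later transplants and, if it does, when. Which rule is right is a clinical decision for the sponsor, and this review takes no position on it.

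The cost is a clarifying amendment of a few sentences. It needs no extra subjects, visits or tests.
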